3.7. Visit Windows

3.7.1. Definition of Study Day

Study day is the day relative to the date of the first dose of study drug. Study Day 1 will be defined as the day of first dose of study drug administration.

Study day will be calculated from the date of first dose of study drug administration and derived as follows:

- For postdose study days: $\text{Assessment Date} - \text{First Dose Date} + 1$
- For days prior to the first dose: $\text{Assessment Date} - \text{First Dose Date}$

The last dose date for an individual study drug will be the end date on study drug administration eCRF for the record where the “subject permanently discontinued” flag is ‘Yes’. The last dose date will be defined as the maximum of the last dose dates of individual study drugs in a treatment group.

If there are subjects for whom the date of last study drug is unknown due to the reason that the subject was lost to follow-up and not able to be contacted, the date of last dose will be estimated using the maximum of nonmissing study drug start or stop dates, visit dates and laboratory collection dates (posttreatment visits and unscheduled visits are not included).

3.7.2. Analysis Windows

Subject visits might not occur on protocol-specified days. Therefore, for the purpose of analysis, observations will be assigned to analysis windows.

In general, the baseline value will be the last nonmissing value on or prior to the first dose date of study drug.

HCV RNA, vital signs, and safety laboratory data collected up to the last dose date + 2 days are considered to be on-treatment data and HCV RNA, vital signs and safety laboratory data collected after the last dose date + 2 days are considered posttreatment data. The analysis windows for on-treatment HCV RNA, vital signs and safety laboratory data are provided in [Table 3-3](#).

Table 3-3. Analysis Windows for On-treatment HCV RNA, Vital Signs and Safety Laboratory Data

Nominal Visit	SOF + RBV 12 Weeks			SOF + RBV 24 Weeks		
	Nominal Day	Lower Limit	Upper Limit	Nominal Day	Lower Limit	Upper Limit
Baseline	1	(none)	1	1	(none)	1
Week 1	7	2	11	7	2	11
Week 2	14	12	21	14	12	21
Week 4	28	22	42	28	22	42
Week 8	56	43	70	56	43	70
Week 12	84	71	≥ 85	84	71	98
Week 16	NA			112	99	126
Week 20				140	127	154
Week 24				168	155	≥ 169

Subjects who participated in the PK Lead-in Phase will immediately roll over into the Treatment Phase with no interruption of study drug administration until the appropriateness of the dose is confirmed by PK and safety data from the PK-Lead-in Phase. These subjects will start at the Week 2 visit of the Treatment Phase. Week 1 records for these subjects will be chosen from Day 7 in the PK Lead-in Phase.

HCV RNA, vital sign, and safety laboratory data collected after the last dose date + 2 days will be assigned to the posttreatment follow-up (FU) visits. Visit windows will be calculated from the last dose date (i.e. FU Day = collection date minus the last dose date) as shown in [Table 3-4](#).

Table 3-4. Analysis Windows for Posttreatment HCV RNA, Body Weight, Height, Vital Sign and Safety Laboratory Data

Nominal FU ^a Visit	HCV RNA, Body weight and Height			Vital Signs and Safety Laboratory Data ^b		
	Nominal FU Day	Lower Limit	Upper Limit	Nominal FU Day	Lower Limit	Upper Limit
FU-4	28	21	69	28	3	30
FU-12	84	70	146	NA	NA	NA
FU-24	168	147	210	NA	NA	NA

a FU-x visit = posttreatment Week-x follow-up visit.

b Vital signs (blood pressure, pulse, respiratory rate, and temperature) and safety labs will only be summarized for the FU-4 visit (up to 30 days after last dose).

3.7.3. Selection of Data in the Event of Multiple Records in an Analysis Window

Depending on the statistical analysis method, single values may be required for each analysis window. For example, change from baseline by visit usually requires a single value, whereas a time-to-event analysis would not require 1 value per analysis window.

If multiple valid nonmissing numeric observations exist in an analysis window, records will be chosen based on the following rules if a single value is needed:

- For baseline, the last available record on or prior to the date of the first dose of study drug will be selected. If there are multiple records with the same time or no time recorded on the same day, average (arithmetic mean) will be used for the baseline value.
- For postbaseline visits:
 - The record closest to the nominal day for that visit will be selected except for HCV RNA posttreatment follow-up visits, for which the latest record in the analysis window will be selected.
 - If there are 2 records that are equidistant from the nominal day, the later record will be selected.
 - If there is more than 1 record on the selected day, the average will be taken, unless otherwise specified.

If multiple valid nonmissing categorical observations exist in a window, records will be selected as follows:

- For baseline, the last available record on or prior to the date of the first dose of study drug will be selected. If there are multiple records with the same time or no time recorded on the same day, the value with the lowest severity will be selected (eg, normal will be selected over abnormal).
- For postbaseline visits, follow the same rules described above for postbaseline numeric observations, except that if there are multiple records on the same day, the most conservative value will be selected (eg, abnormal will be selected over normal).

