**6.4.6. Week 24 ( $\pm$  3 days) – GT-3 Subjects only**

- Perform complete physical examination
- Tanner Staging Assessment
- Vital signs, including body weight and height measurements
- Assessment of AEs and concomitant medications
- Pregnancy prevention counseling including partner pregnancy prevention for male participants (Subjects 12 to < 18 years of age and subjects < 12 years of age at the discretion of the Investigator based on subject's pubertal status)

- Obtain blood samples for:
  - Hematology
  - Chemistry
  - Coagulation tests
  - HCV RNA
  - Viral sequencing (archive)
  - TSH
  - Single PK
- Obtain urine sample for:
  - $\beta$ -hCG pregnancy test for females of childbearing potential only
- Subject completes quality of life survey: Subject is to review questionnaire with a parent/guardian and write/mark answers directly onto the questionnaire
- Review medication compliance with subject and/or parent/guardian.
- GT-3 Subjects should return all bottles and kits at the Week 24 Visit

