#### **6.4.7.            Unscheduled Visit/Early Termination Visit**

A subject should attend an unscheduled visit if requested by the sponsor or the investigator. The assessments are at the investigator's discretion.

The Sponsor/CRO should be informed when a subject comes off treatment due to an adverse event. If a subject discontinues treatment then the assessments outlined below should be performed.

- Perform complete physical examination
- Tanner Pubertal Stage Assessment
- Vital signs, including body weight and height measurements
- Assessment of AEs and concomitant medications
- Pregnancy prevention counseling including partner pregnancy prevention for male participants (Subjects 12 to < 18 years of age and subjects < 12 years of age at the discretion of the Investigator based on subject's pubertal status)

- Obtain blood samples for:
  - Hematology
  - Chemistry
  - Coagulation tests
  - HCV RNA
  - Viral sequencing (archive)
  - TSH
  - Single PK
- Obtain urine sample for:
  - $\beta$ -hCG pregnancy test for females of childbearing potential only
- Subject completes quality of life survey: Subject is to review questionnaire with a parent/guardian and write/mark answers directly onto the questionnaire.
- Review medication compliance with subject and/or parent/guardian.
- Subjects should return all bottles and kits at the Early Termination Visit

All subjects should complete Post-Treatment assessments after early termination, as described in Section 6.5.

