3.5. Missing Data and Outliers

3.5.1. Missing Data

In general, missing data will not be imputed unless methods for handling missing data are specified.

For missing last dosing date of study drug, imputation rules are described in Section 3.7.1. The handling of missing or incomplete dates for adverse event (AE) onset is described in Section 7.1.5.2, and for prior and concomitant medications in Section 7.9.

For analyses of categorical HCV RNA data, missing posttreatment HCV RNA data will have the missing data imputed. Missing on-treatment HCV RNA will have the missing data imputed up to the time of the last dose (for on-treatment displays). If the study day associated with the last dosing date is greater than or equal to the lower bound of a visit window, and the value at the visit is missing, the value will be imputed. If the study day associated with the last dosing date is less than the lower bound of a visit window then the on-treatment value at that visit will remain missing.

If a data point is missing and is preceded and followed in time by values that are “< LLOQ target not detected (TND)”, then the missing data point will be set to “< LLOQ TND”. If a data point is missing and preceded and followed by values that are “< LLOQ detected”, or preceded by “< LLOQ detected” and followed by “< LLOQ TND”, or preceded by “< LLOQ TND” and followed by “< LLOQ detected”, then the missing value will be set to “< LLOQ detected”. In these situations the data point will be termed a bracketed success; otherwise, the data point will be termed a bracketed failure (i.e. \geq LLOQ detected). If a data point is missing and is not bracketed, the missing data point will also be termed a failure (i.e. \geq LLOQ detected) except for SVR24, which will be imputed according to SVR12 status. Success for SVR12 who have no further HCV RNA measurements collected will be counted as a success for SVR24 due to the high correlation between these 2 endpoints.

For the analyses of continuous HCV RNA efficacy data, when and only when a missing HCV RNA value is imputed as < LLOQ TND or < LLOQ detected according to the imputation rule described above, the corresponding continuous value will be imputed to LLOQ - 1 IU/mL. No other imputation will be performed for continuous HCV RNA data.

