4. SUBJECT DISPOSITION

4.1. Subject Enrollment and Disposition

A summary of subject enrollment will be provided by treatment group for each country, investigator within a country, and overall. The summary will present the number and percentage of subjects in the Safety Analysis Set. For each column, the denominator for the percentage calculation will be the total number of subjects analyzed for that column.

A summary of subject disposition will be provided by treatment group. This summary will present the number of subjects screened, the number of subjects enrolled, the number of subjects enrolled but never treated, and the number and percentage of subjects in each of the categories listed below. For the “Treated” category, the denominator for the percentage calculation will be the total number of subjects enrolled for each column. For all other categories, the denominator for the percentage calculation will be the total number of subjects in the Safety Analysis Set for each column.

- Treated (Safety Analysis Set)
- In FAS
- In PK Analysis Set
- Completed study treatment
- Did not complete study treatment with reasons for premature discontinuation of study treatment
- Completed the study
- Did not complete the study with reason for premature discontinuation of study

Among subjects who completed study treatment and who discontinued study treatment, the number and percentage of subjects will be summarized for:

- Who had no HCV posttreatment Week 4 assessment and thereafter (No HCV FU-4 and thereafter)
- Who had HCV posttreatment Week 4 assessment but no HCV posttreatment Week 12 assessment and thereafter (With HCV FU-4 but No FU-12 and thereafter)

If a subject did not have any HCV RNA assessment ≥ 21 days after the last dose of any study drug (i.e. lower bound of FU-4 visit for HCV RNA data), the subject is categorized as having “No HCV FU-4 and thereafter”. If a subject had the HCV FU-4 assessment but did not have any HCV RNA assessment ≥ 70 days after the last dose of any study drug (i.e. lower bound of FU-12 visit for HCV RNA data), the subject is categorized as having “With HCV FU-4 but No FU-12 and thereafter”.

In addition, the total number of subjects who were enrolled, and the number of subjects in each of the disposition categories listed above will be displayed in a flowchart.

The following by-subject listings will be provided by subject ID number in ascending order to support the above summary tables:

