4.2.2. Adherence to Study Drug

The level of adherence to individual study drug will be assessed separately based on the total amount of individual study drug administered relative to the total amount of individual study drug prescribed. In this study, SOF 400 mg tablets, SOF 100 mg tablets, and SOF 50 mg capsules containing granules have been used. For RBV, both REBETOL capsules and REBETOL RBV oral solution have been used. Each capsule contains 200 mg RBV and the oral solution contains 40 mg RBV per mL.

Given the fact that multiple formulations of the study drug have been used in this study, the adherence will be calculated based on the amount of SOF (mg) or RBV (mg) by the following formula:

$$\text{Level of Adherence(\%)} = \left(\frac{\text{Total Amount of Study Drug Administered}}{\text{Total Amount of Study Drug Prescribed at baseline}} \right) \times 100$$

Where the presumed total amount of study drug (mg) administered to a subject will be determined by the data collected on the drug accountability eCRF using the following formula:

$$\text{Total Amount of Study Drug (mg) Administered} = \left(\sum \text{Total Amount of Study Drug (mg) Dispensed} \right) - \left(\sum \text{Total Amount of Study Drug (mg) Returned} \right)$$

Note: If calculated adherence is greater than 100%, the result will be set to 100%.

The total amount of prescribed SOF (mg) for 12 weeks and 24 weeks are as follows:

Age Group and Body Weight	SOF Daily Dose	Total Amount of SOF Prescribed for 12 Weeks	Total Amount of SOF Prescribed for 24 Weeks
12 to <18 years any weight	400 mg/day	33600 mg	67200 mg
6 to <12 years any weight	200 mg/day	16800 mg	33600 mg
3 to <6 years weighing ≥17 kg	200 mg/day	16800 mg	33600 mg
3 to < 6 years weighing <17 kg	150 mg/day	12600 mg	25200 mg

RBV was prescribed by weight at baseline for all subjects. The total amount of RBV (mg) prescribed for 12 weeks and 24 weeks is as follows:

Body Weight kg (lbs.)	RBV Daily Dose	RBV Number of Capsules	Total Amount of RBV Prescribed for 12 Weeks	Total Amount of RBV Prescribed for 24 Weeks
<47 (<103)	15 mg/kg/day	Use Oral Solution. Divided dose in the morning and evening.	1,260 mg/kg	2,520 mg/kg
47-49 (103-108)	600 mg/day	1 × 200-mg capsules A.M. 2 × 200-mg capsules P.M.	252 capsules (50400 mg)	504 capsules (100800 mg)
50-65 (110 – 143)	800 mg/day	2 × 200-mg capsules A.M. 2 × 200-mg capsules P.M.	336 capsules (67200 mg)	672 capsules (134400 mg)

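### A compliant end-of-treatment visit at +3 days falls past the SAP's +2-day on-treatment cut-off, and its HCV RNA value enters no analysis window

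*SAP*

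**What the plan says.** **Visit timing.** Protocol 6.4.4 gives the Week 12 visit, the last treatment visit for GT-2, a tolerance of 3 days either way. Protocol 6.4.6 does the same for GT-3: "Week 24 ( $\pm$ 3 days) – GT-3 Subjects only". For early stoppers, Protocol 6.4.7 says "If a subject discontinues treatment then the assessments outlined below should be performed", with HCV RNA on the list, but sets no number of days after the last dose.

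**Cut-off.** SAP 3.7.2: "HCV RNA, vital signs, and safety laboratory data collected up to the last dose date + 2 days are considered to be on-treatment data". Anything later goes to follow-up: "data collected after the last dose date + 2 days will be assigned to the posttreatment follow-up (FU) visits", with FU day equal to collection date minus last dose date. SAP 3.7.1 fixes that date: "The last dose date will be defined as the maximum of the last dose dates of individual study drugs in a treatment group".

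**Follow-up windows.** In SAP Table 3-4 the first HCV RNA window, FU-4, covers days 21 to 69. SAP 4.1 repeats the lower limit: "21 days after the last dose of any study drug (i.e. lower bound of FU-4 visit for HCV RNA data". For vital signs and safety laboratory data, FU-4 covers days 3 to 30.

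**Missing values.** Under SAP 3.5.1 a missing on-treatment HCV RNA category is imputed when the last dose day reaches the lower bound of the visit window. It becomes below LLOQ only if the values before and after are both below LLOQ; "otherwise, the data point will be termed a bracketed failure", meaning at or above LLOQ. A value that is not bracketed at all is also a failure.

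**The concern.** The protocol's visit tolerance is one day wider than the SAP's on-treatment period, and the next HCV RNA window does not open for more than two weeks after that. A sample taken on time under the protocol can therefore sit between the two sets of windows. It may still appear in a listing, but it is left out of every windowed summary.

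At stake is the percentage of subjects with HCV RNA below LLOQ by visit, a secondary endpoint in SAP 6.2.1, at its end-of-treatment row and in the on-treatment graph. A child who was suppressed at the last visit and relapsed by FU-4 could be displayed as not suppressed at end of treatment, although a sample showing suppression was collected. Another table could count the same child as a relapser, a category that requires suppression at end of treatment.

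**Working it through.** **Inputs**
- Visit tolerance: ±3 days (Protocol 6.4.4, 6.4.6).
- On-treatment cut-off: last dose + 2 days (SAP 3.7.2).
- First HCV RNA follow-up window: FU days 21–69 (SAP Table 3-4).
- Prescribed SOF totals: "400 mg/day 33600 mg 67200 mg" for the daily dose, 12 weeks and 24 weeks (SAP 4.2.2).
- Lower bounds of the end-of-treatment windows: Day 71 for Week 12 (GT-2) and Day 155 for Week 24 (SAP Table 3-3).

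**Course length.** 33600 / 400 = 84 days and 67200 / 400 = 168 days. These reproduce the nominal Days 84 and 168 in Table 3-3.

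**Where each permitted visit day goes.** The GT-2 visit may fall on Days 81–87 (84 ± 3), which is 7 days. A day is on-treatment if it is no later than last dose + 2.

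| Last dose | Last on-treatment day | Permitted visit days with no HCV RNA window |
|---|---|---|
| Day 81 | 83 | 84–87 (4 of 7) |
| Day 82 | 84 | 85–87 (3 of 7) |
| Day 83 | 85 | 86–87 (2 of 7) |
| Day 84 | 86 | 87 (1 of 7 = 14%) |
| Day 85 | 87 | none |

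For GT-3 add 84 to every day: with a last dose on Day 168, visits on Days 165–170 map to Week 24, and Day 171 is FU day 171 − 168 = 3, with no window. The open upper limits in Table 3-3 (≥ 85, ≥ 169) do not help, because that table covers on-treatment data only.

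**Width of the gap.** FU days 3 to 20 inclusive: 20 − 3 + 1 = 18 days without an HCV RNA window. An Early Termination sample can fall on any of them.

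**What is imputed.** 84 ≥ 71 and 168 ≥ 155, so the missing end-of-treatment category must be imputed. Take the preceding visit (Week 8 or Week 20) as below LLOQ, the uncaptured sample as below LLOQ, and only windowed values as brackets:
- FU-4 below LLOQ: imputed below LLOQ, which is correct. This includes a relapse first seen at FU-12.
- FU-4 at or above LLOQ: imputed at or above LLOQ, contrary to the sample.
- No later value: not bracketed, so imputed at or above LLOQ, contrary to the sample.

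**Other displays.** The collected value drops out of the continuous HCV RNA summary. Laboratory and vital-sign values from FU day 3 leave the Week 12/24 row and enter FU-4 (days 3–30), where a record nearer day 28 displaces them. If the 4-week visit is held on FU days 31–33 (28 + 5 = 33, allowed by Protocol 6.5.1), the FU day 3 values stand in as FU-4. The liver-event table in SAP 7.2.2.3 also stops at 2 days after the last dose.

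**Effect of one child.** With about 50 subjects per age group, one misclassified child moves an age-group total by 1/50 = 2 points. Genotype group sizes are not given; assuming 5 to 25, the shift is 1/25 = 4 to 1/5 = 20 points.

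**The case against.** The strongest reply is that the false failure needs several things together: a visit on exactly the third late day, dosing that stopped on schedule, and an FU-4 value at or above LLOQ or no later value. This stands. The prescribed totals in SAP 4.2.2 are an adherence denominator, not a stop-date rule. The last dose date is the later of the two drugs, and unused drug is returned at the visit itself. A child who takes either drug to within 2 days of the visit loses nothing.

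It can also be said that SAP 3.5.1 speaks only of values before and after in time. If the uncaptured sample may be the later value, the imputation is correct. The SAP does not settle this. SAP 6.2.2 assigns values by analysis window, which favours the windowed reading, so an ambiguity remains to be closed.

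A reader might infer more than the documents support:
- **SVR12 or relapse is biased.** SVR12 uses the FU-12 window (days 70–146). The relapse denominator in SAP 6.2.2 uses the last observed on-treatment value, so a suppressed Week 8 or Week 20 result keeps the relapser in it.
- **Safety findings are lost.** Treatment-emergent laboratory abnormalities run to last dose + 30 days (SAP 7.2.2.1).
- **The end-of-treatment weight and height change is lost.** The +2-day sentence and Table 3-3 do not name weight or height. The procedures tables group them with vital signs and footnote b of Table 3-4 does not, so the rule is unclear and loss is not shown.
- **Breakthrough is misrecorded as relapse.** Calling a first positive value three days off drug post-treatment is a boundary convention; any cut-off creates such cases.
- **Two of seven days are lost after a full course.** That needs visits counted from Day 85. Protocol 3.2.2 places them at the end of the week, and Table 3-3 puts Week 12 at Day 84.

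**Conclusion.** The mismatch is real and should be corrected, but its reach is narrow. After a full 84- or 168-day course, 1 of the 7 permitted visit days (14%) yields an HCV RNA value with no window. More days are lost if dosing ends 1 to 3 days early, and none if it continues to within 2 days of the visit. The 14% is a share of calendar days, not of subjects; the documents give no attendance or stop-date distribution from which to estimate the latter.

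Affected: the by-visit HCV RNA table and graph, the continuous HCV RNA summary, the Week 12/24 laboratory and vital-sign rows, and the on-treatment liver-event table. A false not-suppressed result at end of treatment further requires FU-4 at or above LLOQ or no later value, and a windowed-only reading of the bracketing rule. SVR12, the relapse denominator and the treatment-emergent laboratory summaries stand as planned.

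**What to change.** 1. In SAP 3.7.2 and 7.2.2.3, set the on-treatment cut-off at last dose + 3 days. Start the FU-4 laboratory and vital-sign window at day 4. With a last dose on Day 84 or 168, every permitted visit day is then captured.
2. The wider cut-off alone does not cover courses that end early: with a last dose on Day 83, 82 or 81, the last 1, 2 or 3 permitted days are still lost. So add a label rule. When no record falls in the subject's end-of-treatment analysis window (the one containing the last dose day), assign the HCV RNA sample labelled Week 12 (GT-2), Week 24 (GT-3) or Early Termination to end of treatment, provided it was taken by FU day 20. That limit keeps it from also entering FU-4. Flag it in the listing. Use it for the by-visit displays only, leaving the relapse denominator as SAP 6.2.2 has it.
3. State in SAP 3.5.1 that an observed sample outside all windows may serve as a bracketing value.

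The cost is SAP wording and window code; no new data are needed. The downside is that a few end-of-treatment values will have been taken some days off drug, up to 20 for an Early Termination sample, and a late one could already reflect relapse. The flag lets a reader see which they are.
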